3.7.3.3 Physical Examination and Vital Signs

A full physical examination will be conducted at screening and a directed/targeted physical examination will be conducted at the subsequent visits as noted in [Table 3.7-1](#). The full physical examination will include an evaluation of the following body systems: head and neck; ears, eyes, nose, and throat; thorax; abdomen; genitourinary; extremities; neurological; and skin and mucosae. There is no need for a genitourinary exam if the subject has confirmation from a gynecologist or urologist of a gender- and age-appropriate exam conducted within 1 year. For purposes of this trial, the directed/targeted physical examination will include an abdominal examination.

Whenever possible, the same individual should perform all physical examinations for any individual subject throughout the course of the trial (for consistency of assessment). For trial sites in the United States, individuals performing the physical examination must be permitted to do so by local regulations, must be listed on the Food and Drug Administration (FDA) Form 1572 as principal investigator or subinvestigator, and must be listed on the trial site delegation of authority form as performing this function.

Vital signs (blood pressure, heart rate, temperature, and respiratory rate) will be measured at the time points specified in [Table 3.7-1](#). Blood pressure and heart rate measurements will be made in the supine and sitting positions after the subject has been in each position for at least 5 minutes. Vital signs should be measured before blood samples for PK analysis are collected, when applicable.

3.7.3.4 Electrocardiogram Assessments

The 12-lead ECGs will be performed in the supine position.

At the sparse blood sampling sites, standard safety ECGs will be conducted during the screening period; predose on Day 1; 1 to 4 hours postdose on Day 1, Day 8, Week 2, Week 6, and Week 12/End of Treatment; and at the 30-day post-treatment follow-up.

At the robust blood sampling sites, triplicate ECGs will be recorded on Day 1 and Week 6 at predose (prior to the morning dose) and at 2, 4, and 8 hours after the morning dose. The 3 ECG replicates will be extracted from a 5-minute “ECG window” (typically, the last 5 minutes of the 15-minute period when the subject is maintained in a supine position). There will be at least 1 minute between each ECG. Baseline will be the average of the 3 ECG measurements conducted in triplicate at predose on Day 1. Blood samples for PK analysis should be taken immediately following the triplicate ECG assessments. Additional standard safety ECGs will be conducted during the screening period; 1 to

Protocol 341-201-00004

4 hours postdose on Day 8, Week 2, and Week 12/End of Treatment; and at the 30-day post-treatment follow-up visit.

Subjects should be monitored for potentially clinically significant ECG results. Any abnormalities considered by the investigator to be clinically significant are to be recorded as AEs on the AE screen in eSource.

The ECGs should be performed before blood sample collection, when applicable. A central ECG service will be utilized for reading all ECGs. Additional ECGs may be conducted based on local regulatory requirements, as needed.

3.7.3.5 Other Safety Assessments

3.7.3.5.1 Ileocolonoscopy With Biopsy

After completion of a daily diary for 7 days during the screening period, subjects will undergo bowel preparation for 3 days (consisting of 2 days of dietary modifications and 1 day of cleansing bowel preparation) and then an ileocolonoscopy with biopsy will be performed. The ileocolonoscopy should be performed within 7 to 10 days prior to Day 1. An ileocolonoscopy with biopsy will be performed again at Week 12/End of Treatment, after another 3 days of bowel preparation. The 3-day bowel preparation should be approximately 4 days prior to the Week 12 (eg, Day 80 through Day 82) visit date; this is to ensure that subjects are still taking IMP for these assessments. An ileocolonoscopy with biopsy will be conducted up to approximately 1 day prior to the Week 12 (eg, Day 83) visit date.

The readings of these ileocolonoscopies will be conducted by a central reading facility. Detailed language on the collection of the ileocolonoscopy data will be provided in a study manual. Detailed language on the readings of the ileocolonoscopies will be provided in an ileocolonoscopy charter.

3.7.4 Prior and Concomitant Medications

The investigator will record all medications and therapies taken by the subject from 30 days prior to signing of informed consent through the end of the evaluation period (defined as the time period during which subjects are evaluated for primary and/or secondary objectives) in the electronic source records (eSource). The investigator will record all medications and therapies taken by the subject for treatment of an AE or which caused an AE until the end of the trial (defined as the last date of contact) in eSource.

Protocol 341-201-00004

3.7.5 Pharmacokinetic/Pharmacodynamic Assessments

3.7.5.1 Pharmacokinetic Assessments

3.7.5.1.1 Pharmacokinetic Blood Samples

Blood samples (4 mL, NaF/KOx) will be collected and processed into plasma to determine the concentrations of OPS-2071 and its metabolite, M34101, at the time points outlined below. The concentrations of additional metabolites that are not identified in the protocol may also be determined if needed.

Two different PK blood sampling schemes, an extensive (robust) and a sparse sampling scheme, will be utilized at different trial sites. Forty subjects from selected trial sites will be required for robust blood sampling.

At the sparse blood sampling trial sites, blood samples for PK analysis will be collected on Day 1 at predose and on Day 1, Week 2, Week 6, and Week 12/End of Treatment 1 to 4 hours after the morning dose at the same time as the collection of blood samples for clinical laboratory tests.

A total of 40 subjects at the robust blood sampling trial sites will receive OPS-2071 or placebo according to the randomization plan. At the robust blood sampling trial sites, blood samples for PK analysis will be collected from 40 subjects immediately following the triplicate ECG assessments, on Day 1 and Week 6 at predose and at 2, 4, and 8 hours after the morning dose. Additional blood samples for PK analysis will be collected at the robust blood sampling trial sites at Week 2 and Week 12/End of Treatment 1 to 4 hours after the morning dose at the same time as the collection of blood samples for clinical laboratory tests. Robust blood sampling will be completed once there are 40 subjects that have completed the trial on-treatment. Once robust blood sampling has been completed, these trial sites will continue to complete sparse blood sampling.

Processing, storage, and shipping instructions for blood samples for PK analysis are provided in [Appendix 1](#).

3.7.5.1.2 Pharmacokinetic Urine Samples

No urine samples will be collected for PK analysis.

Protocol 341-201-00004

3.7.5.2 Pharmacodynamic Assessments

A blood sample will be collected and processed into plasma to assess CRP. If CRP is not elevated on Day 1, there is no need for any further CRP assessments. In addition, a fecal sample will be collected to assess FCP.

No formal pharmacodynamic (PD) assessments are planned.

3.7.6 Fecal Microbiota

Fecal samples will be collected at the time points defined in [Table 3.7-1](#) for the stool microbiology testing, FCP, and microbiota assessment. During screening, the fecal sample should be collected prior to the bowel preparation and ileocolonoscopy. Collection and processing instructions will be provided separately.

Fecal samples for the microbiota assessment will be analyzed and changes relative to baseline in the abundance and taxonomical profile will be evaluated. Questions that are applicable to the fecal microbiota assessment will be included in the questionnaire that is part of each subject's diary. Data from the microbiota assessment will be reported separately.

3.7.7 Future Biospecimen Research Sample Collection

A whole blood sample (up to 10 mL) for FBR will be collected only from subjects who consent to this sample collection.

Research performed on this sample may include genetic analyses (eg, DNA, gene expression profiling [ribonucleic acid], proteomics, metabolomics, and/or the measurement of other analytes). Such research is for biomarker testing to address emergent questions not described elsewhere in the protocol (as part of the main trial) and will only be conducted on specimens from appropriately consented subjects. The objective of collecting specimens for FBR is to explore and identify biomarkers that inform the scientific understanding of diseases and/or their therapeutic treatments.

NOTE: If subjects consent to the optional blood sample collection for FBR, then the second aliquot of blood samples for PK analysis collected from these subjects may be stored and used for this research.

Processing, storage, and shipping instructions for blood samples for FBR are provided in [Appendix 1](#).

Protocol 341-201-00004

3.7.8 End of Treatment/End of Trial

If a subject discontinues IMP before Week 12, the last date that the subject received IMP will be recorded as the End of Treatment. See [Section 3.8](#) for more information on the End of Treatment rules for this trial.

The end of trial date is defined as the last date of contact from the 30-day post-treatment follow-up visit screen in eSource for the last subject completing or withdrawing from the trial.

3.7.9 Independent Data Monitoring Committee

For this trial, an Independent Data Monitoring Committee (IDMC; also known as a Data Safety Monitoring Board) will be established. The role of the IDMC and the various criteria adhered to will be delineated in detail in a separate IDMC charter document, but in general, this group will meet on a regular basis to ensure the safe and ethical treatment of trial subjects, the scientific integrity of the trial, and that the trial is conducted within the bounds of ethical medical practice. The IDMC may make recommendations to the sponsor to amend or terminate the trial based on grounds of safety, futility, or greater than expected efficacy as defined by the accepted statistical practices and procedures to be detailed in their charter.

3.8 Stopping Rules, Withdrawal Criteria, and Procedures

3.8.1 Entire Trial or Treatment Arm(s)

If the sponsor terminates or suspends the trial for any reason, prompt notification will be given to investigators, IRBs/IEC, and regulatory authorities in accordance with regulatory requirements.

3.8.2 Individual Site

Individual trial site participation may be discontinued by the sponsor, the investigator, or the IRB/IEC if judged to be necessary for medical, safety, regulatory, ethical or other reasons consistent with applicable laws, regulations, and GCP. The investigator will notify the sponsor promptly if the trial is terminated by the investigator or the IRB/IEC at the site.

Protocol 341-201-00004

3.8.3 Individual Subject Discontinuation

3.8.3.1 Treatment Interruption

All attempts should be made to avoid treatment interruption during the trial. For subjects who have an interruption of treatment, the investigator or designee will contact the sponsor at the earliest possible time by telephone. The sponsor should be notified when there is a planned or inadvertent treatment interruption of 4 days or more in a 7-day period. The investigator and sponsor will come as quickly as possible to a joint decision regarding the subject's continuation in the trial. This decision will be documented by the investigator and the sponsor, and reviewed by the trial site monitor. The treatment interruption will be recorded in eSource and also recorded as a protocol deviation (Section 3.13).

3.8.3.2 Treatment Discontinuation and/or Trial Discontinuation

After randomization, a subject may stop treatment permanently for a variety of reasons. Treatment discontinuations may be initiated by a subject who is not satisfied with treatment or may become medically necessary due to AEs, required treatment with a disallowed medication or therapy, or other issues, as determined by the investigator. Subjects who increase dosages of baseline Crohn's disease medications or take a new therapy for Crohn's disease during the trial will be considered as treatment failures (nonresponders) in the efficacy analysis. However, based on investigator's judgement, these subjects may continue their IMP treatment, or discontinue their IMP treatment, but are encouraged to stay in the trial for scheduled study assessments. Each investigator should comprehensively review the circumstances for each subject and refer to Section 3.8.3.5 for additional information. A subject who discontinues treatment will be recorded as an IMP discontinuation in eSource and have an End of Treatment visit. Subjects who discontinue from the trial will have an End of Treatment visit, which should be scheduled as soon as possible after the subject's last dose of IMP, and a 30-day post-treatment follow-up visit to collect the assessments defined in the schedule of assessments (Table 3.7-1).

Subjects who discontinue IMP, but remain on their stable baseline Crohn's medication, will complete an End of Treatment visit and are allowed to stay in the trial and have efficacy evaluations at Week 12.

If a subject discontinues from the trial prematurely, the reason must be fully evaluated and recorded appropriately in source documents and in eSource. If the subject is being withdrawn because of an AE, that AE should be indicated as the reason for withdrawal.

Protocol 341-201-00004

All subjects have the right to withdraw at any point during treatment without prejudice. The investigator can discontinue a subject's participation in the trial at any time if medically necessary. Subjects whose consents are completely withdrawn will be discontinued from the trial and the reason will be recorded in eSource. These subjects will complete the End of Treatment visit.

Subjects who are discontinued from the trial will not be replaced.

3.8.3.3 Documenting Reasons for Treatment Discontinuation

A subject may discontinue IMP for a number of reasons, including those listed below:

- Reasons related to AE:
 - Subject decides to discontinue because of annoyance or discomfort due to a nonserious AE which is not otherwise determined to be an undue hazard
 - Continuing IMP places the subject at undue risk as determined by the investigator (eg, a safety concern that is possibly, probably, or likely related to IMP)
 - SAE
 - Other potentially IMP-related safety concerns or AEs
- Death
- Reasons unrelated to medical condition (provide detail and review AE history with subject)
- Withdrawal of informed consent (complete written withdrawal of consent form)
- Lost to follow-up
- Pregnancy (see [Section 5.5](#))
- Termination of all or part of the trial by the sponsor

Adverse events that are stopping rules to be reported directly to the medical monitor include the following:

- 1) A confirmed prolongation of QTcF with an absolute value > 500 msec or any QTcF interval prolonged 60 msec or greater compared to baseline
- 2) Hemoglobin count of < 8.0 g/dL
- 3) Platelet count of 100000 μ L or less
- 4) Discontinuation of treatment should be considered for liver function test abnormalities if:
 - a) ALT or AST $> 8 \times$ ULN
 - b) ALT or AST $> 5 \times$ ULN for more than 2 weeks
 - c) ALT or AST $> 3 \times$ ULN and total bilirubin $> 2 \times$ ULN or international normalized ratio > 1.5

Protocol 341-201-00004

- d) ALT or AST $> 3 \times$ ULN with the appearance of fatigue, nausea, vomiting, right upper quadrant pain or tenderness, fever, rash, and/or eosinophilia ($> 5\%$)
- 5) New onset *C difficile* or enteric infection
- 6) Any IMP-related clinically significant event that jeopardizes the safety or health of the subject
- 7) Any IMP-related clinically significant event, uncontrolled by optimal medical care
- 8) Any toxicity related to IMP administration, requiring the delay of administration of IMP > 5 days

If the subject discontinues IMP due to an AE, the investigator, or other trial personnel, will make every effort to follow the event until it has resolved or stabilized. Refer to [Section 3.8.3.2](#) for requirements in the event of IMP discontinuation.

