3.4.2 Inclusion Criteria

Subjects are required to meet the inclusion criteria presented in [Table 3.4.2-1](#).

Table 3.4.2-1 Inclusion Criteria	
1.	Male and female subjects between the ages of 18 and 70 years, inclusive.
2.	Diagnosis of Crohn's disease localized in the ileum and/or colon, with active mucosal inflammation and visible lesion(s), documented by centrally read ileocolonoscopy and a SES-CD ≥ 6 (≥ 4 for isolated ileal disease).
3.	Subjects who do not have an optimal response ^a (daily stool frequency > 3 and pain score > 1) to their current ongoing treatment of biologics (eg, first anti-TNF- α monoclonal antibody), immunosuppressants, low-dose steroids, or 5-ASA formulations.
4.	Subjects who are on stable Crohn's disease medications for at least 4 weeks.
5.	Subjects with a CDAI score between 180 and 450 points, inclusive.
6.	Subjects who are willing and able to follow the trial protocol and have signed informed consent.

^aThe minimum duration of prior treatment required for a subject to be considered as having a nonoptimal response includes completing at least the recommended induction regimen for approved biologics and/or treatment at a therapeutic dose for a stable duration that would be anticipated to result in improvement (ie, 12 weeks for azathioprine, 4 weeks for methotrexate). Prior treatment examples and their minimum durations can be found in [Appendix 4](#).

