3.4.3 Exclusion Criteria

Subjects will be excluded if they meet any of the exclusion criteria in [Table 3.4.3-1](#).

Table 3.4.3-1 Exclusion Criteria	
1.	Females who are breast-feeding and/or who have a positive pregnancy test result prior to receiving IMP.
2.	Sexually active males or WOCBP who do not agree to practice 2 different methods of birth control or remain abstinent during the trial and for 30 days after the last dose of IMP. If employing birth control, 2 of the following precautions must be used: vasectomy, tubal ligation, intrauterine device, birth control pill, birth control implant, or birth control depot injection. A vaginal diaphragm, condom with spermicide, or sponge with spermicide may also be used as measures to prevent pregnancy, but must be used in combination with at least one of the previous methods.
3.	Subjects taking any nonsteroidal anti-inflammatory drugs that cannot be stopped or replaced.
4.	Use of prednisone or prednisolone > 30 mg/day or budesonide > 9 mg/day within 4 weeks prior to screening; or intravenous steroids within 4 weeks prior to screening.
5.	Subjects taking antithrombotic drugs.
6.	Subjects with symptomatic bowel stenosis, fistula, or stoma; or with more than 2 bowel resections.
7.	Subjects with short bowel syndrome.
8.	Subjects with known existing aortic aneurysm, or who are at risk for an aortic aneurysm, such as subjects with peripheral atherosclerotic vascular diseases, uncontrolled hypertension, certain genetic conditions such as Marfan syndrome and Ehlers-Danlos syndrome, and elderly subjects (over the age of 70).
9.	Subjects with known or suspected (family history, unexplained syncope) long QT syndrome or QTcF > 470 msec for females or > 450 msec for males at baseline.

Protocol 341-201-00004

Table 3.4.3-1 Exclusion Criteria

10.	Subjects with inadequate organ function, as follows: 
 • Serum creatinine $> 1.5 \times \text{ULN}$ • AST or ALT levels $> 1.5 \times \text{ULN}$ • Total bilirubin $> 1.5 \times \text{ULN}$. Elevated unconjugated bilirubin related to Gilbert's syndrome is allowed.
11.	Use of antibiotics (eg, metronidazole, rifaximin, tinidazole, ciprofloxacin, clarithromycin) within 15 days prior to screening or for greater than 2 months within the past year. A short course (maximum of 5 days) of antibiotics will be permitted during the trial, as needed, for indications other than Crohn's disease.

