12.	Known hypersensitivity to quinolones or other significant adverse reaction to quinolones.
13.	Conditions or circumstances that could prevent completion of the trial according to the judgment of the investigator, including an uncontrolled comorbidity, heart condition, or dysfunction of any other organ; peripheral neuropathy; known arrhythmias, atrial fibrillation, or paroxysmal tachycardia; history of myasthenia gravis; history of drug or alcohol abuse, mental illness, or noncompliance with treatments or visits; or known immune-deficiency. ^a
14.	HIV infection, viral hepatitis, prior organ transplant, or malignant disease that is not in remission for at least 3 years, with the exception of basal cell carcinoma.
15.	Subjects who have used any investigational drug within 2 months prior to screening.
16.	Blood donation in the last 2 months.
17.	Use of inhibitors of UGT1A1 and UGT1A9 (eg, Silybin, diclofenac, mycophenolic acid, efavirenz, regorafenib) and BCRP (eg, Estrone, 17 β -estradiol, flavonoids, herb extracts, gefitinib, imatinib, tamoxifen, novobiocin, nelfinavir, ritonavir, dipyridamole, fumitremorgin C, Ko143, cyclosporine, curcumin, eltrombopag, omeprazole, ivermectin).
18.	Subjects with a history of treatment failure with 2 or more biologics. ^b
19.	Subjects with risk factors for tendon rupture (ie, psoriasis, ankylosing spondylitis, competitive athletes, renal failure, diabetes mellitus) or who have a history of tendon rupture and/or ongoing tendinopathy.
20.	Subjects with systolic blood pressure $> 150 \text{ mmHg}$ or diastolic blood pressure $> 90 \text{ mmHg}$.
21.	Subjects taking quinidine, procainamide, disopyramide, encainide, flecainide, sotalol, amiodarone, ibutilide, dronedarone, or propafenone.

BCRP = breast cancer resistance protein; HIV = human immunodeficiency virus; QTcF = QT interval corrected for heart rate by the Fridericia formula; WOCBP = women of childbearing potential.

^aSubjects that test positive for marijuana or for confirmed prescription medications (eg, opioid analgesics) may be permitted to be enrolled if they have no evidence of a substance use disorder. Allowance for subjects testing positive for marijuana or confirmed prescription medications at screening requires explicit approval from the medical monitor.

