Appendix 2 Crohn's Disease Activity Index (CDAI)

Clinical or Laboratory Variable	Weighting Factor
Sum of the number of liquid or soft stools assessed each day over 7 days	x 2
Sum of abdominal pain grade (graded from 0 - 3 on severity) assessed each day over 7 days	x 5
Sum of general well-being, subjectively assessed from 0 (well) to 4 (terrible) each day over 7 days	x 7
Presence of complications*	x 20
Taking Lomotil or opiates for diarrhea	x 30
Presence of an abdominal mass (0 as none, 2 as questionable, 5 as definite)	x 10
Absolute hematocrit deviation of 47 – percentage value for men	x 6
Absolute hematocrit deviation of 42 – percentage value for women	x 6
Percentage deviation from standard weight	x 1

*One point each is added for each set of complications:

- the presence of joint pains (arthralgia) or frank arthritis
- inflammation of the iris or uveitis
- presence of erythema nodosum, pyoderma gangrenosum, or aphthous ulcers
- anal fissures, fistulae or abscesses
- other fistulae
- fever during the previous week.

Protocol 341-201-00004

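### The hemoglobin and platelet stopping rules have no matching entry limit, so a subject already past one at screening can be randomized and dosed

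*Protocol*

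**What the plan says.** Protocol 3.8.3.3 introduces a list with the words "Adverse events that are stopping rules to be reported directly to the medical monitor include the following". Rule 2 is "Hemoglobin count of < 8.0 g/dL". Rule 3 begins "Platelet count of 100000" and applies at that value or below. Both are absolute values. Rule 1 combines an absolute QTcF limit of 500 msec with "any QTcF interval prolonged 60 msec or greater compared to baseline", and rule 5 is confined to infections of new onset.

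On entry, exclusion 10 in Table 3.4.3-1 ("Subjects with inadequate organ function, as follows") sets limits of 1.5 x ULN for creatinine, AST or ALT, and total bilirubin. Exclusion 9 sets QTcF limits of 450 msec (men) and 470 msec (women). No inclusion or exclusion criterion names hemoglobin or platelets. The nearest is exclusion 13, "Conditions or circumstances that could prevent completion of the trial according to the judgment of the investigator", which lists examples but no blood count.

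Hematology, including hemoglobin and platelets, is drawn at screening (3.7.1.1 and Table 3.7.3.2-1). On Day 1 it is repeated only after a significant change in concomitant medication (3.7.1.2 and 3.7.3.2). The next scheduled sample is Day 8, on treatment (3.7.1.3). Section 3.7.1.2 has every subject who satisfies all the criteria randomized and dosed.

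**The concern.** A stopping limit marks a value at which the sponsor has doubts about continuing the drug. Unless an entry limit excludes that value, the plan permits starting the drug where it would otherwise question going on. The QTcF and liver rules avoid this and the two hematology rules do not.

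Two consequences follow. First, safety: a subject with severe anemia or a low platelet count can start a 12-week course of an investigational fluoroquinolone. The Protocol's own introduction names bloody stools and anemia as features of Crohn's disease, so a low hemoglobin at screening is not far-fetched. Second, reporting: if the unchanged value is acted on at Day 8 or later, section 5.1 makes a laboratory value an adverse event when it leads to discontinuation. The stop may then be counted in the table of TEAEs leading to discontinuation of IMP (Protocol 7.6.1, SAP 9.2), although the value predates the drug.

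The primary comparison is not the issue. Sections 3.8.3.2, 3.8.3.5 and 7.3.1 allow subjects who stop IMP to remain and be assessed at Week 12.

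**Working it through.** The plan states no figure on this point, so there is none to reproduce. The check has two parts.

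**1. Stopping limits against entry limits (Protocol 3.8.3.3 against Tables 3.4.2-1 and 3.4.3-1)**

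| Quantity | Entry limit | Stopping limit | Entry limit excludes the stopping value? |
|---|---|---|---|
| QTcF, absolute | 450 msec (men), 470 msec (women) | > 500 msec | Yes |
| AST/ALT | 1.5 x ULN | > 3, > 5 or > 8 x ULN, depending on the sub-rule | Yes |
| Hemoglobin | None | < 8.0 g/dL | No |
| Platelets | None | 100000 or less | No |

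**2. Could the CDAI criterion act as an indirect hemoglobin limit?**

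Inclusion 5 ("Subjects with a CDAI score between 180 and 450 points, inclusive") is the only entry criterion that uses a hematology value. Appendix 2 weights the hematocrit item ("Absolute hematocrit deviation of 47" for men, 42 for women) by 6:

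- Men: points = 6 x (47 − Hct)
- Women: points = 6 x (42 − Hct)

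The documents do not link hemoglobin to hematocrit. I assume Hct (%) = k x hemoglobin (g/dL), with k = 3.0 and a range of 2.8 to 3.4. At hemoglobin 8.0 g/dL:

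| k | Hct (%) | Points, men | Points, women |
|---|---|---|---|
| 2.8 | 22.4 | 6 x 24.6 = 147.6 | 6 x 19.6 = 117.6 |
| 3.0 | 24.0 | 6 x 23.0 = 138.0 | 6 x 18.0 = 108.0 |
| 3.4 | 27.2 | 6 x 19.8 = 118.8 | 6 x 14.8 = 88.8 |

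As a share of the 180 points needed:

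- Men: 118.8/180 = 66.0% to 147.6/180 = 82.0%
- Women: 88.8/180 = 49.3% to 117.6/180 = 65.3%

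The upper bound does not exclude these subjects either. The most points any case above uses is 147.6, which leaves 450 − 147.6 = 302.4 for all other items.

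As an illustration, inclusion 3 asks for more than 3 stools a day and a pain score above 1. Suppose these are 7-day averages of the CDAI diary items. The smallest qualifying weekly sums are then 22 and 8, worth 2 x 22 + 5 x 8 = 84 points. At k = 3.0 the total is 138 + 84 = 222 for a man and 108 + 84 = 192 for a woman, both above 180 before any other item is counted. The lowest case, a woman at k = 3.4, reaches 88.8 + 84 = 172.8 and passes 180 once well-being averages 1 a day (7 x 7 = 49 points).

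So the CDAI criterion favors entry of an anemic subject. Platelets are not a CDAI item, so it says nothing about them.

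**The case against.** The strongest reply is that the list is headed as adverse events, and section 5.1 asks whether an abnormal laboratory value is a clinically significant change from that subject's baseline. A stable low value is then not clearly an adverse event and not clearly a trigger. This stands as a limit: a stop at Day 8 is possible, not certain. It does not answer the entry problem, and it leaves room for two sites to treat the same value differently.

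A second reply is that exclusion 13 already covers such a subject. Investigators review every laboratory report and eligibility is verified again on Day 1. A careful investigator may well exclude. But the criterion rests on judgment and names neither value, and the plan did not leave QTcF, liver or renal values to judgment.

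Third, adverse events are recorded from consent, so a medically relevant low value at screening could be reported to the medical monitor before dosing. That is an inference from a section about stopping treatment, and nothing in it bars randomization.

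Fourth, the absolute 500 msec limit and the liver limits carry no baseline condition either. That is correct. The distinguishing feature of rules 2 and 3 is the missing entry limit, more than the missing baseline wording.

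Finally, the numbers are probably small, the CDAI arithmetic gives no frequency, and SAP section 11 records that the trial ended with three randomized subjects and that the planned analyses will not be performed. All of this stands and limits the practical effect here. The criteria as written remain inconsistent, which matters for any restart or reuse of the design.

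**Conclusion.** The concern holds. As written, a subject with screening hemoglobin below 8.0 g/dL or platelets of 100000 or less can meet every entry criterion and be dosed unless the investigator invokes exclusion 13. This follows from the text alone and needs no assumption.

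The documents give no basis for estimating how many subjects would be affected. The one quantity that can be calculated is how little the CDAI criterion protects. It depends on the assumed hematocrit-to-hemoglobin ratio, but the direction does not, since the weight of 6 always adds points as hematocrit falls below the reference.

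This is a modest safety inconsistency that should be corrected because doing so is cheap. It does not threaten the primary analysis.

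**What to change.** Add to exclusion 10, in Table 3.4.3-1 and in the synopsis, a screening hemoglobin below 8.0 g/dL or a screening platelet count of 100000 or less. The screening hematology already collected supplies both values.

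This is a minimum. It removes the direct conflict but creates no margin: a subject at hemoglobin 8.0 g/dL or platelets of 100001 still enters and could cross the limit by Day 8 through ordinary variation, and the screening sample may be up to 28 days old. If the sponsor wants a margin like those for QTcF and AST/ALT, it should set stricter entry values.

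The cost is one line in each place by amendment and a few more screen failures, with no new test or visit.
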